7.8.4. Electrocardiogram

ECG measurements and change from baseline in ECG measurements, including heart rate (bpm), QT interval (msec), PR interval (msec), QRS interval (msec), RR interval (msec), QTcB interval (msec), and QTcF interval (msec), will be summarized descriptively in the safety population.

To identify potential clinically significant QTcF results, the numbers and percentages of subjects in the safety population who experience confirmed post-baseline absolute QTcF values >450 msec, >480 msec, and >500 msec will be summarized, as will the numbers and percentages of subjects who experience confirmed increases from baseline in QTcF ≥30 msec and ≥60 msec. In addition, a shift table comparing the baseline overall ECG interpretations, based on investigator interpretation, of normal, abnormal – not clinically significant, and abnormal – clinically significant to the investigator interpretation at each post-baseline visit will be presented.

A listing of ECG measurements and investigator-reported ECG interpretations will be presented.

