4.3.2. Individual Subject Stopping Criteria

Discontinuation of Study Drug

Individual subjects must pause or discontinue treatment with study drug in the following settings:

- Development or worsening of lupus manifestations requiring introduction of certain prohibited medications or prohibited dosages of background drugs, when continuation of the study drug would place the subject at risk, as determined by the Investigator or Medical Monitor; see §8.2.2.
- Clinically significant abnormal laboratory results or AEs which rule out continuation of the study drug, as determined by the Investigator or the Medical Monitor.
- Infection with SARS-CoV-2 during the Treatment Period; the Medical Monitor must approve the resumption of study drug dosing for any subject with confirmed (viral test positive) or suspected COVID-19 infection.
- Grade ≥ 3 infection (e.g., pneumonia, sepsis) which cannot be sufficiently controlled within an adequate timeframe by anti-infective treatment or would put the subject at risk for continued participation in the trial, as determined by the Investigator or the Medical Monitor.
- Inclusion or exclusion criteria violation that was noted after the subject started study drug, AND the Investigator and/or Medical Monitor determine that continuation of the study drug would place the subject at risk.
- Development of an electrocardiogram (ECG) change considered clinically significant and with reasonable possibility of relationship to study drug; or a confirmed absolute QT interval corrected for heart rate using Fridericia's correction formula (QTcF) value > 500 msec or confirmed increase of ≥ 60 msec from Baseline (i.e., if a subject's QTcF increases from Baseline ≥ 60 msec, the Investigator will evaluate, confirm the value, and treatment should be stopped).
- Development of active or latent tuberculosis (TB) at any time during the study; a subject with active or latent TB must pause dosing with blinded study drug; dosing can only be resumed following initiation of appropriate treatment and with the approval of the Medical Monitor.
- Pregnancy while on study drug.
- Malignancy, except for localized non-melanoma skin cancer or carcinoma in situ of the cervix; if localized cancer is surgically excised with clear margins, dosing may resume following consultation with the Medical Monitor.

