6.7. Description of Study Procedures Medical and Disease History, Demographics

Includes medical, surgical, and disease histories. Disease history includes date of diagnosis, prior treatment and responses, and remarkable toxicities. Demographic information includes sex, age, and self-reported race/ethnicity. Ongoing medical conditions will be documented, together with medications and therapeutic procedures that are expected to continue during the study. At Screening, a detailed history of prior SLE activity will be obtained.

Physical Examination

Complete physical examination will be performed at intervals designated in the schedule of assessments, and will include examination of head, eyes, ears, nose and throat, lungs, heart, abdomen, joints, muscle and soft tissues, neurologic system, skin and lymph nodes.

Physical examination that is adequate to assess SLE disease activity by BILAG and SLEDAI-2K 30 will be performed at each visit at which those assessment tools are employed, as designated in the schedule of assessments and detailed in the Procedures Manual.

Physical examination directed based on the review of system and/or AEs will be performed at planned and unplanned visits as indicated.

Vital Signs

Vital signs (temperature, blood pressure, pulse rate, and respiratory rate) will be obtained with the subject at the times indicated in the summary of assessments. Unless otherwise specified, all vital signs should be measured after the subject has been resting, preferably for at least 5 minutes, and prior to invasive procedures such as drawing blood.

Weight

Body weight (kilograms) will be obtained with the patient's shoes and jacket or coat removed. Total dose of blinded study drug administered will be based on the weight at Baseline (Day 1) unless weight has changed from baseline by more than 10%. In that case, total dose of blinded study drug administered will be based on the most current weight.

Electrocardiogram

All ECGs should be obtained in accordance with the central ECG instructions in the Procedures Manual. Subjects are to be resting, preferably in the supine position for approximately 5 minutes before each ECG.

TB Screening

The imaging and diagnostic tests for TB screening should be interpreted in the context of the subject's epidemiology, history, exam findings, etc., and it is the responsibility of the Investigator to determine if a subject has previous, active, or latent TB.

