ADA, Anti-drug antibodies; AEI, Adverse event of interest: BILAG, British Isles Lupus Assessment Group index; CLASI, Cutaneous Lupus Erythematosus Disease Area and Severity Index; EoS, End of study; EoT, End of treatment; FACIT-F, Functional Assessment of Chronic Illness Therapy-Fatigue; PhGA, Physician's Global Assessment of SLE Disease Activity; PK, Pharmacokinetics; PtGA, Patient's Global Assessment of Disease Activity; SDI, Systemic Lupus International Collaborating Clinics/American College of Rheumatology (SLICC/ACR) Damage Index; SF-36, Short Form-36; SLE, Systemic lupus erythematosus; SLEDAI, Systemic Lupus Erythematosus Disease Activity Index; TSH, Thyroid stimulating hormone.

PROTOCOL AIS-A03

Notes:

On the days of study drug administration, all assessments and procedures must be performed prior to dosing except where otherwise specified.

- 2 Assessments should also be performed in the event of early discontinuation.
- 3 Visit held only for subjects in the Dense PK subset.
- 4 Investigator's screening eligibility assessment must be reviewed and confirmed by Sponsor or designee. Refer to Inclusion Criterion 4.
- 5 Perform prior to randomization and study-drug dosing.
- 6 This requirement may be met with documentation of a previous chest x-ray performed within 3 months of Screening.
- 7 Complete physical examination required at Screening, Baseline, and EoS or early discontinuation.
- 8 A problem-oriented exam may be performed at the physician's discretion; however, at applicable visits, physical examination required for SLEDAI and BILAG assessment must be performed.
- Obtain pre-dose, and then at 10 minutes (\pm 10 min) following completion of infusion.
- 10 BILAG, SLEDAI-2K 30 (or SLEDAI-2K on Day 15 per footnote 12), PhGA, CLASI, Screening (see footnote 11) and Day 15 (see footnote 12).
- 11 SLEDAI-2K 30, BILAG, and PhGA; lupus history should be recorded at Screening.
- 12 SLEDAI-2K, PhGA.
- 13 Skin photography should be performed as indicated if any abnormalities are recorded on CLASI.
- 14 PtGA, SF-36, FACIT-F (13-item). Note: Patient's assessments should be completed before physician's assessment.
- 15 Collect blood and urine samples using kit provided by the central laboratory; refer to APPENDIX 2.
- 16 In addition to standard safety lab evaluations, includes TSH.
- 17 Collect samples using kit provided by the central laboratory; refer to APPENDIX 2.

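### SAP 7.8.4 counts only *confirmed* QTcF exceedances without defining the term, and three of its five categories have no confirmation step in either document

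*SAP*

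**What the plan says.** SAP 7.8.4 gives the table a screening purpose: "To identify potential clinically significant QTcF results". It counts subjects "who experience confirmed post-baseline absolute QTcF values >450 msec, >480 msec, and >500 msec will be summarized" and also "subjects who experience confirmed increases from baseline in QTcF ≥30 msec and ≥60 msec". The qualifier therefore attaches to all five categories. The SAP does not say how many tracings are needed, over what interval, who confirms, or how an exceedance that was never rechecked is classified.

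The word occurs in one other relevant place, the individual stopping criteria in Protocol 4.3.2: "confirmed absolute QT interval corrected for heart rate using Fridericia's correction formula (QTcF) value > 500 msec or confirmed increase of ≥ 60 msec". The action is spelled out only for the change criterion: "if a subject's QTcF increases from Baseline ≥ 60 msec, the Investigator will evaluate, confirm the value, and treatment should be stopped". No method or timing is given there either.

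ECGs are scheduled in Protocol Table 1 (reproduced as SAP Table 8) on Days 1, 85 and 155, with the note "Obtain pre-dose, and then at 10 minutes" after the infusion, and once on Day 197. Protocol 6.7 adds: "All ECGs should be obtained in accordance with the central ECG instructions in the Procedures Manual". That manual is not among the documents.

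**The concern.** A qualifier that suits a stopping decision has been carried into a screening count. For a stopping decision it is reasonable to verify a reading before acting on it. For a count meant to pick up possible prolongation, the same word can turn a missing recheck into an absence of the event, which is the less cautious direction.

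Safety is the primary objective, and SAP 3.2 names abnormal ECG parameters as a safety endpoint. Protocol 4.4.4 says this is the first study to dose for longer than 4 weeks. With 76 subjects randomized (SAP 4.1), one or two subjects moving in or out of a row would change how it reads. Two programmers working from the same sentence could also produce different tables.

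**Working it through.** The documents state no QTcF rate and no expected count, so there is no plan figure to reproduce. The check is mainly a comparison of passages.

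**1. Thresholds against confirmation steps.**

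| SAP 7.8.4 category | Confirmation in Protocol 4.3.2 | Method or timing in either document |
|---|---|---|
| >450 msec | none | none |
| >480 msec | none | none |
| >500 msec | value must be confirmed | none |
| increase ≥30 msec | none | none |
| increase ≥60 msec | investigator confirms | none |

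Categories with no confirmation step: 5 − 2 = 3.

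**2. Can the scheduled ECGs act as repeats?** Scheduled post-baseline time points are Day 1 post-dose (1), Day 85 pre- and post-dose (2), Day 155 pre- and post-dose (2) and Day 197 (1): 1 + 2 + 2 + 1 = 6. Only the two pre-dose ECGs, on Days 85 and 155, are followed by another scheduled ECG the same day. The other 6 − 2 = 4 are not. After Day 1 the next scheduled ECG is 84 days later (85 − 1), after Day 85 post-dose 70 days (155 − 85), after Day 155 post-dose 42 days (197 − 155), and after Day 197 there is none. An unscheduled ECG is required at early stop of study drug (Protocol 4.3.2), and other unscheduled evaluations are discretionary (Protocol 6). Neither is tied to a QTcF value.

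**3. Interaction with SAP Section 12.** For visit-based analyses, the earlier of two same-day values is kept. Applied here, that would remove the post-dose ECGs on Days 85 and 155. SAP Table 5 also starts its first post-baseline ECG window on Day 2, so the Day 1 post-dose ECG has no post-baseline window. The SAP does not say whether these rules govern the outlier table.

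**4. Comparison with other safety tables.** SAP 7.8.2 takes the worst post-baseline laboratory grade and peak liver values. SAP 7.8.3 counts vital signs crossing limits. Neither asks for confirmation. SAP Section 13 resolves missing adverse-event severity, relationship and seriousness cautiously. Among these numeric threshold tables, only QTcF requires confirmation.

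**5. Illustration (p, r and c are assumptions).** Subjects per arm: n = 76 / 2 = 38. Let p be the share with any exceedance, r the share of exceedances that are repeated, and c the share of repeats still above the threshold.

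- Any-exceedance count = n × p
- Confirmed count = n × p × r × c

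For p = 10%, the any-exceedance count is 38 × 0.10 = 3.8. The confirmed count is:

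- r = 0: 0
- r = 0.5, c = 0.5: 3.8 × 0.25 = 0.95
- r = 0.5, c = 1: 3.8 × 0.5 = 1.9
- r = 1, c = 0.5: 1.9
- r = 1, c = 1: 3.8

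For p = 5% and 20%, the any-exceedance counts are 38 × 0.05 = 1.9 and 38 × 0.20 = 7.6. The confirmed count runs from 0 up to the same number.

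**6. How far the definition matters.** A simulation of one baseline and six post-baseline values per subject, with independent normal errors, gave these shares of subjects with an increase of at least 30 msec:

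| Error SD (assumed) | True shift (assumed) | Any ECG | At least two ECGs | Both ECGs on Day 85 or both on Day 155 |
|---|---|---|---|---|
| 8 msec | 0 | 2.0% | 0.3% | 0.1% |
| 8 msec | 20 msec | 50.2% | 29.5% | 13.1% |
| 12 msec | 0 | 15.0% | 5.1% | 1.5% |
| 12 msec | 20 msec | 64.0% | 43% | 22.0% |

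The definition changes the count severalfold, and the zero-shift rows show that an any-exceedance count also picks up noise.

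**The case against.** The strongest reply is that *confirmed* need not mean a second tracing above the limit. Protocol 4.3.2 speaks of the investigator confirming the value, which could be verification of the reading, and central ECG instructions leave room for an over-read. Under either meaning a single QTcF of 470 msec could be counted. This stands, and it is why the understatement is conditional on how the word is programmed.

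A reader might go further and infer that no repeat ECG exists, that every scheduled ECG is a single tracing, or that three rows must come out at or near zero. The documents support none of these. Repeat triggers and the number of tracings per time point may be set in the Procedures Manual. Table 1 and its notes give time points, not tracings. On Days 85 and 155 a post-dose ECG could confirm a pre-dose exceedance if the SAP allowed it.

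Nor do prolonged values vanish from reporting. QTcF values and changes are summarized descriptively, investigator interpretations are shown as shifts, all ECG measurements are listed (SAP 7.8.4), and clinically significant ECG results are analysed as adverse events (SAP 7.8.1). Safety is descriptive, so no test depends on these counts. But means dilute individual outliers, the shift table does not use QTcF thresholds, and a listing gives no incidence by arm.

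Finally, the qualifier screens out artefact, and step 6 shows that this has some value. It supports keeping confirmed rows. It does not support making them the only rows, since noise affects both arms and the placebo column shows its level.

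**Conclusion.** The point holds as a gap in definition with a possible bias in one direction. All five categories depend on an undefined word, and three of the five have no confirmation step in the two documents. If the word is programmed as a repeated exceedance, an exceedance that was not repeated becomes a non-event and the outlier counts can be too low.

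The size cannot be determined from the documents. The illustrative range of 0 to 3.8 subjects per arm rests on an assumed 10% exceedance rate, about 38 subjects per arm and unknown repeat behaviour; its upper end means no loss at all. The loss would be confined to the outlier counts. At >500 msec and ≥60 msec the SAP uses the protocol's own qualifier, so there the gap is the missing definition and the missing rule for a value that was never rechecked.

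**What to change.** In SAP 7.8.4:

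- Make the main count any post-baseline exceedance in each of the five categories, using the worst QTcF and the largest increase over all scheduled, unscheduled, pre-dose and post-dose ECGs after the first dose, including Day 1 post-dose.
- State that the Section 12 same-day rule does not apply to this table.
- Keep confirmed >500 msec and confirmed increases of at least 60 msec as additional rows, and define *confirmed*: what counts as confirmation, within what interval, by whom, and how an exceedance that was not rechecked is shown.

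This takes a few sentences and a few table rows, with no new data. The downside is that some counts may reflect isolated or artefactual readings and look slightly less favourable; the confirmed rows and the placebo column help the reader judge that. The change concerns tabulation only and leaves the stopping criterion in Protocol 4.3.2 as it is.

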7.8.5. Physical Examinations

Complete physical examinations will be performed at intervals designated in the scheduled of assessments (Appendix 15.2) and will include examination of head, eyes, ears, nose and throat, lungs, abdomen, joints, muscle and soft tissues, neurologic system, skin, and lymph nodes.

Clinically relevant findings identified during a physical examination will be reported and summarized as AEs.

7.9. Analysis of Biomarkers

Descriptive summaries of the absolute, change from baseline, and percent change from baseline

. Additionally, the incidence of subjects with shifts from abnormal baseline values to normal values at EOT in clinical biomarkers will be presented for each treatment group.

7.10. Analysis of Pharmacokinetic Endpoints

ALPN-101 concentration data will be summarized by visit for the PK population. Mean concentration data will also be presented graphically. In summaries of concentration data, concentrations that are reported below the lower limit of quantitation (BLOQ) will be treated as missing.

The PK data obtained in dense PK subset subjects will be analyzed using non-compartmental analysis. The PK parameters including C_{max} , AUC, $t_{1/2}$, and C_{trough} will be determined based on the available data. Descriptive statistics (n, arithmetic mean, standard deviation, % coefficient of variation (CV), min, median, max, geometric mean, and geometric %CV) will be calculated for the PK parameters. For individual PK parameter estimation, BLOQ will be treated as missing if

the value occurs after T_{max} . Investigational population PK modeling and exposure-response analysis is outside the scope of this SAP.

7.11. Analysis of Immunogenicity Endpoints

The incidence of ADA positive to study drug will be summarized by visit and overall for each treatment group for the ADA population. The min and max of the ADA titer value will also be presented. For subjects who are ADA positive, the incidence of NAb positive will be summarized by visit and overall for each treatment group.

8. CHANGES IN ANALYSIS FROM PROTOCOL

Analyses described in this plan are consistent with the protocol-specified analyses. Changes made to the planned analyses described in this SAP will be documented in an SAP amendment or described in the Clinical Study Report.

9. INTERIM ANALYSIS

An administrative interim analysis may be performed when approximately 50% of subjects have completed assessments through Week 24 (Day 169).

10. DATA REVIEW COMMITTEE

Cumulative safety data will be reviewed by a Data Monitoring Committee (DMC), which will provide recommendations regarding study conduct, if indicated. Roles and responsibilities of the DMC are defined in the DMC charter. The specifications for the presentation of study data in the DMC report is defined in a separate analysis plan.

11. MULTIPLICITY ADJUSTMENT

No adjustments for multiplicity will be applied in the analyses of data from this first clinical study of APN-101 in subjects with active SLE.

13	Day 169/EOT	169	166	172	160	≤183
EOS	Day 197/EOS	197	194	200	184	EOS visit date

1 Indicates Day 29 visit window definition applicable to efficacy assessments scheduled for Day 15

2 Indicates Day 29 visit window definition applicable to efficacy assessments NOT scheduled for Day 15

Notes: EOS=End of study; EOT=End of treatment.

There will be no windowing for the SDI endpoint as this endpoint is only collected at Day 1, end of treatment, and end of study.

Table 5: Visit Windows for ECG Data

Visit Visit Number Label		•		efined Visit dow	Analysis Defined Window		
Number	Labei	Day	From	To	From	To	
1	Baseline	1	1	1	≤1		
7	Day 85	85	82	88	2	≤120	
12	Day 155	155	152	158	121	≤176	
EOS	Day 197/EOS	197	194	200	177	EOS visit date	

13. DATA HANDLING

Data handling rules for specific missing efficacy and safety data and missing and partial dates is provided below.

Missing Lab Data for BILAG Renal and Hematological Organ System Scoring:

In the event there is missing lab data for the renal or hematological BILAG organ systems at a particular visit, the preceding visits lab data will be used in the derivation of the renal and hematological BILAG grading. If the preceding visits lab data is also missing, then the lab data will be missing and a BILAG grade for that organ system will not be derived.

Missing BILAG D or E Grades After a Missed Visit:

Due to constraints within the electronic clinical outcome assessment vendor system, BILAG grades of D and E cannot be scored after a subject has a missed visit. Organ system grades for these non-missing visit cases will be derived by carrying forward the previous non-missing D or E grade for these organ systems. This does not apply to grades of A, B, or C.

Table 6: Dummy Coding for Multiple Imputation Modeling

Region	Strata2d	Strata3d
North America/Western Europe	0	0
Eastern Europe	1	0
Asia	0	1

Region	Strata2d	Strata3d
North America/Western Europe is	the reference region	

• Step 2: A CMH test will be conducted for each imputed dataset on the Day 169 endpoint. The Wilson-Hilferty transformation will be applied to the CMH general association test statistic to create a normally distributed statistic with a mean=0 and standard deviation=1. Generic SAS code is provided below:

```
proc freq data=d_log;
tables strata1n*strata2n*treatment*resp_D169 / CMH;
ods output CMH=cmh;
by Imputation;
run;
```

Where strata1n and strata2n are the stratification factors for concomitant oral immunosuppressive therapy use at enrollment and geographic region from the Interactive Response Technology system for randomization.

```
data cmh_wh; set cmh (where=(AltHypothesis="General Association")); cmh_value_wh=((VALUE/DF)**(1/3) - (1-2/(9*DF)))/SQRT(2/(9*DF)); cmh_sterr_wh = 1.0; run;
```

• Step 3: Combine the transformed values from the 100 imputed datasets using PROC MIANALYZE. The combined p-value for the CMH test will be obtained as the upper-tailed p-value from the test produced by PROC MIANALYZE.

```
proc mianalyze data=cmh_wh;
  ods output parameterestimates = est1;
  modeleffects cmh_value_wh;
  stderr cmh_sterr_wh;
run;

data fin_cmh; set est1;
  if tValue > 0 then Probt_upper = Probt/2;
  else Probt_upper = 1-probt/2;
run;
```

Missing Safety Information:

For analyses of AE data, events with missing severity grade will be imputed as Grade 3 for analysis. Similarly, AEs with missing relationship to study drug will be imputed as drug-related. If no designation of event seriousness is available, the AE will be considered serious.

Missing and Partial Dates:

Algorithms applied for imputing partial and missing date values are described below:

Table 7: Imputation of Partial and Missing Date Values

Partial/Missing Start or Stop Date	Imputed Start Date	Imputed Stop Date
Missing year, month, and day	Date of randomization visit	
Missing month and day, and the year is present	Date of randomization visit if the year is the same as the year of randomization date, else January 1 of the start year.	December 31 of that year
Missing day, but year and month are present	Date of randomization visit if the year and month are the same as the year and month of randomization date, else the 1st of the start month.	Last day of that month
Missing month, but year and day are present	Assume day is also missing and impute as above	Missing month imputed as December

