- Any new medication started during the study for SLE. The following exceptions are allowable:
 - Corticosteroid burst as specified above
 - Medication may be reduced or temporarily discontinued for safety reasons and then started again. This would not be considered a new medication
- Other restricted medications taken any time during the study:
 - Biologics (e.g., abatacept, anifrolumab, atacicept, belatacept, belimumab, obinutuzumab, ocrelizumab, rituximab, telitacicept)
 - Investigational agents

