7.2. Demographics and Baseline Characteristics and Medications

Descriptive summaries of demographics and baseline characteristics will be presented by treatment group for all randomized subjects. No formal statistical comparisons between the treatment arms will be performed. A by-subject listing of demographic and key baseline data will be provided.

History of significant non-SLE conditions and current medical conditions reported at screening and/or baseline will be summarized by Medical Dictionary for Regulatory Activities (MedDRA) system organ class (SOC) and preferred term (PT). The number and percentage of subjects in each treatment group of the safety population who reported each SOC and PT will be reported.

The number and percentage of unique subjects in the safety population who report use of prior and concomitant medications will be summarized separately by treatment group and for all subjects combined. Prior medications are medications with start and end dates prior to the date of the first dose of study drug. A medication that was started prior to the first dose of study drug and continued after first dose of study or that has a first dose date after the first dose of study drug will be summarized as a concomitant medication. An additional table summarizing all concomitant medications which are initiated on or after the date of the first administration of study drug will be provided. Concomitant medications for treatment of SLE, including concomitant corticosteroids, will be summarized separately. A single subject will be counted once, regardless of the number of times a specific medication was used.

Oral corticosteroid use during the study will be summarized for the mITT population using the following variables:

- Incidence of subjects oral corticosteroid use
- Incidence of subjects with changes in oral corticosteroid use
- Total exposure to oral corticosteroid use (area under the oral corticosteroid exposure curve while on study treatment) using prednisone-equivalent doses as described in Appendix 15.6
- Duration (days) of oral corticosteroid use while on study treatment

Rescue medications will be summarized for the mITT population for each treatment group and for all subjects combined.

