7.8.1. Treatment-Emergent Adverse Events

AEs will be recorded at all scheduled and unscheduled visits during the study. Summaries will be presented for TEAEs. In this study, signs and symptoms of SLE activity are captured in the disease activity assessments and will not be reported as AEs. Clinically significant changes in physical exam findings, laboratory test results, and ECG results will be recorded and analyzed as AEs. The incidence, seriousness, and severity of TEAEs and the relationship of the events to study drug will be used to assess safety.

All AEs terms will be classified using MedDRA and reported based on system organ classes and preferred terms. Adverse event severity will be graded using Common Terminology Criteria for Adverse Events (CTCAE), version 5.0. AEIs will be reviewed by the medical monitor lead.

In general, the incidence of AEs will be summarized by the number and the percentage of unique subjects in the safety population who experiencing an event. As such, subjects who report the

same event on multiple occasions will only be counted once. A by-subject listing of all AEs reported will be provided. Rules for the imputation of missing and partial AE dates and missing designations of AE severity, relatedness and seriousness are defined in Section 13.

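### SAP Table 7 has no exception for drugs known to be ongoing before first dose, so some background drugs with missing or partial start dates are dated to Day 1 and could count as new SLE medication

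*SAP*

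**What the plan says.** The date rules are in SAP Section 13 under their own sub-heading, separate from the missing-safety-data rules, and open in general terms: "Algorithms applied for imputing partial and missing date values are described below". Table 7 then fixes the start date as follows:

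- "Missing year, month, and day": the randomisation visit, unconditionally.
- Year known, month and day missing: "Date of randomization visit if the year is the same as the year of randomization date", and otherwise 1 January of the start year.
- Year and month known, day missing: "Date of randomization visit if the year and month are the same as the year and month of randomization date", and otherwise the first of the start month.
- Year and day known, month missing: handled as if the day were missing too.

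Three other parts of the SAP use medication start dates or the idea of a new drug:

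- Section 7.2 plans an additional table of "concomitant medications which are initiated on or after the date of the first administration of study drug".
- Section 6.21 lists among the treatment-failure criteria "Any new medication started during the study for SLE", and also the addition of an antimalarial. Failure applies to the visits that follow the medication.
- Section 7.4.2 names restricted or rescue medication as intercurrent event IE2 and scores it as non-response for binary primary and secondary endpoints.

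The one explicit pointer to Section 13 for dates is in the adverse-event section: "Rules for the imputation of missing and partial AE dates and missing designations of AE severity, relatedness and seriousness are defined in Section 13". Sections 6.21 and 7.2 do not refer to it.

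**The concern.** Imputing an unknown start to Day 1 is cautious for an adverse event, because it makes the event treatment-emergent. For a drug the subject was already taking, the same rule gives a date known to be wrong. Every subject in this trial has such a drug: Protocol 5.1 (criterion 7) requires at least one antimalarial or immunosuppressant at entry.

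At minimum, the SAP 7.2 table of drugs begun on study is misstated. If the imputed date is also what decides whether a drug is new under SAP 6.21, an unchanged background drug becomes a rescue event on Day 1. It then covers every post-baseline visit, including Day 169, and the composite strategy overrides the observed SRI-4 and BICLA results. With enrolment stopped at 76 (SAP 4.1), a few such subjects are visible in the response rates.

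**Working it through.** **1. Which start dates Table 7 moves to Day 1.** Randomisation and first dose both fall on Day 1 (Protocol 6.2 and Table 1), so a start imputed to the randomisation visit meets the 7.2 condition. Applying the rule row by row:

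| Recorded start of a background drug | Imputed start | Result |
|---|---|---|
| Nothing recorded | Randomisation visit | Day 1 |
| Year only, randomisation year | Randomisation visit | Day 1 |
| Year only, any earlier year | 1 January of that year | Before dosing |
| Month and year, randomisation month | Randomisation visit | Day 1 |
| Month and year, earlier month | First of that month | Before dosing |

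**2. Reach of the year-only row.** Assume randomisation is spread evenly over the calendar year. A drug begun L months earlier then falls in the randomisation year with probability max(0, 1 − L/12). That is 75% for 3 months, 50% for 6, 25% for 9, and 0 for 12 or more. For drugs begun a year or more before randomisation, only the fully missing row matters.

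**3. Reach of the month-and-year row.** The listed immunosuppressants must be stable for 4 weeks before Screening (Protocol 5.1), and screening data are due at least 14 days before randomisation (Protocol 6.1). That is 28 + 14 = 42 days, longer than any month, so this row should not catch them. Antimalarials and corticosteroids need stability only from Screening to Baseline and can be caught.

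**4. The plan's own power figures.** Inputs from SAP 4.2: 65 per arm, two-sided chi-square, alpha 0.05, placebo 40% (SRI-4) and 20% (BICLA). Write p̄ for the mean of p0 and p1, and q = 1 − p:

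power = Φ{ [ (p1 − p0) − 1.96·√(2p̄q̄/n) ] / √[(p0q0 + p1q1)/n] }

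- SRI-4, 40% v 65%: (0.25 − 1.96 × 0.0876)/0.0848 = 0.923, power 82.2% (SAP Table 1: 82%).
- BICLA, 20% v 45%: (0.25 − 1.96 × 0.0822)/0.0792 = 1.124, power 86.9% (SAP Table 1: 87%).

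**5. Size at the actual enrolment.** An even split of 76 gives 38 per arm (assumption). One would-be responder lost moves that arm by 1/38 = 2.6 points.

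Let f be the share of subjects wrongly set to non-responder. The documents give no value, so f is an assumption. If f is equal in both arms, each rate becomes p(1 − f) and the difference 25(1 − f) points:

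| f | Subjects (76f) | Difference | SRI-4 power, 38/arm | BICLA power, 38/arm |
|---|---|---|---|---|
| 0 | 0 | 25.0 | 59.1% | 64.8% |
| 2% | 1.5 | 24.5 | 57.2% | 63.5% |
| 5% | 3.8 | 23.75 | 54.5% | 61.4% |
| 10% | 7.6 | 22.5 | 50.2% | 58.0% |

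Only would-be responders are lost. At the planning rates the two-arm averages are (40 + 65)/2 = 52.5% for SRI-4 and (20 + 45)/2 = 32.5% for BICLA. So 1.5–3.8 flagged subjects mean about 0.8–2.0 lost SRI-4 responders and 0.5–1.2 lost BICLA responders over both arms.

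Chance imbalance can push either way. With f = 5% in one arm only, the SRI-4 difference is 65 × 0.95 − 40 = 21.75 points if the arm is active, and 65 − 40 × 0.95 = 27 points if it is placebo.

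**The case against.** A reader might infer that any missing or partial start date turns a long-standing SLE drug into an on-study start and the subject into a non-responder. The documents do not support that, for two reasons. The fallback branches of Table 7 keep every drug with a known earlier year or month before dosing. And SAP 6.21 never says that imputed dates decide what is new: its wording about additions and increases from baseline can be applied to the documented baseline therapy.

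The other side has further points. Baseline use is recorded independently of start dates: ongoing medications are documented at entry (Protocol 6.7) and updated on Day 1 (Protocol 6.2), and immunosuppressant or higher-dose corticosteroid use is a stratification factor. The planned listing of restricted medications (SAP 7.2) could expose a false event. The prior-versus-concomitant split is unaffected for a continuing drug, which is concomitant either way. No document shows that start dates are often incomplete. The public SAP text also has gaps, so a medication rule in text not shown cannot be excluded.

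These points narrow the problem and make the endpoint consequence conditional. They do not remove it. Table 7 is general in wording and is the only date rule visible for medications, while 7.2 needs start dates. For non-SLE drugs used at baseline, Protocol 8.2.1 asks only for name and indication, so a missing start date is foreseeable there. That affects the 7.2 table, not the rescue-medication event.

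**Conclusion.** The concern holds in a limited form. Table 7 assigns a wrong start date to a background drug when the start is fully missing, is year-only in the randomisation year, or is month-and-year in the randomisation month. The misstatement of the 7.2 table follows directly from the text. The false non-response for SRI-4 and BICLA follows only if imputed dates feed 6.21, which the SAP leaves open.

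The expected effect is modest. Start dates of background drugs precede randomisation, so the error should be balanced on average and mainly dilutes the difference, by 0.5–1.25 points on 25 for an assumed f of 2–5%. In a trial of about 38 per arm, chance imbalance of one or two responders is still noticeable. SRI-4 and BICLA are the primary efficacy endpoints; the trial's primary objective is safety, which this point does not touch. The frequency and the even split are assumptions.

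**What to change.** Add a short exception to SAP Section 13 and a cross-reference in 6.21 and 7.2:

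- Any medication documented as ongoing at Screening or Baseline is classed as pre-existing and given a start before first dose, whatever part of the date is missing.
- For such a drug, the imputed start cannot trigger IE2. A documented dose increase or other 6.21 criterion still can.
- An imputed start may not fall after a known stop date.
- Adverse events, and medications not documented at baseline, keep the Day 1 imputation; those medications can still trigger IE2.

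Two broader remedies should be avoided. Restricting Table 7 to adverse events would remove the only visible date rule for medications, including stop dates. Barring every imputed date from triggering IE2 would let real rescue drugs with partial dates pass as no event.

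The cost is a few SAP sentences and one derivation. It is best done before unblinding, with a blinded count of background drugs that have an imputed Day 1 start. After that point, document the change by the route in SAP Section 8 and show the results under both rules.
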